#### **2.2.2. Secondary Endpoints - Efficacy**

##### **Efficacy in Patients with Late-stage HAT**

A patient with late-stage HAT will be considered as a success at 6 months and at 12 months if the CSF WBC is equal to or below 20/ $\mu$ L and in the absence of trypanosomes, rescue treatment and signs or symptoms suggesting a relapse at the visit in question or previously.

If the patient does not have a lumbar puncture at 6 months, the outcome of the lumbar puncture at 12 months will be used. If the patient does not have a lumbar puncture at 12 months and if a lumbar puncture is performed at 18 months, the outcome at 18 months will be used. Otherwise, the outcome at 6 months will be used. If the patient has no post-treatment lumbar puncture, s/he will be considered as a failure. Patients lost to follow-up and deaths, regardless of the cause, will be considered as failures.

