##### **Endpoints in Patients with Early- or Intermediate-stage HAT**

Two efficacy endpoints will be used for patients with early- and intermediate-stage HAT: the outcome at 12 months and the outcome at 18 months after receiving treatment. A patient will be considered as a success at 12 months if the patient is alive with no evidence of trypanosomes in any body fluid and if the CSF

WBC is equal to or less than 20/ $\mu$ L. A patient with no parasitological evidence of relapse, but with a CSF WBC above 20/ $\mu$ L or who, in the Investigator's opinion, requires rescue treatment, will be considered as a relapse. A patient who refuses the lumbar puncture at 12 months will be classified as a probable cure (success) in the absence of any clinical signs or symptoms suggestive of THA or with another obvious aetiology, provided that the outcome was favourable, i.e. a CSF WBC equal to or less than 5/ $\mu$ L, at 6 months. Death for any reason, patients lost to follow-up and not retrieved or patients with no post-treatment lumbar puncture will be considered as failures, with the exception of patients who fled the region due to armed conflict or natural disaster. For memory, patients who fled the region due to armed conflict or natural disaster will not be included in the mITT population and will therefore not be taken into account in the calculation of the success rate. A patient with early- or intermediate-stage HAT will be considered as a **success** at 18 months if the CSF WBC is equal to or below 20/ $\mu$ L and in the absence of trypanosomes, rescue treatment and signs or symptoms suggestive of a relapse. If the patient does not have a lumbar puncture at 18 months, the outcome at 6 months or at 12 months will be used.

A patient with early- or intermediate-stage HAT will be considered as a success at 6 months and at 12 months if the CSF WBC is equal to or less than 20/ $\mu$ L and in the absence of trypanosomes, rescue treatment and signs or symptoms suggestive of a relapse. If the patient does not have a lumbar puncture at 6 months, the outcome at 12 months and, if necessary, at 18 months will be used. If the patient does not have a lumbar puncture at 12 months, the outcome at 18 months will be used and, if necessary, the outcome at 6 months will be used. If no post-treatment lumbar punctures were performed, the outcome will be considered as unfavourable.

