
| Derivation algorithm for stage 1 and intermediate stage (month 18)   | Derivation algorithm for stage 2 (Month 18)  |
|--|--|
| 
Earlier (before M18) unfavorable outcome: increase of WBC in CSF at M6 or M12 with respect to EOH
 
⇒ YES ⇒ 9: Failure (stop)
 
↓
 
NO (no information or no earlier unfavorable assessment)
 
↓
 
Patient has clinical signs or symptoms at M18 evoking a failure
 
⇒ YES ⇒ 10: Failure (stop)
 
↓
 
NO (no clinical signs or symptoms evoking a relapse at M18)
 
↓
 
WBC in CSF ≤ 20 at M12 or absence of LP at M12 and for both cases no increase WBC in CSF at M6 with respect to EOH and no sign and symptoms at M18 evoking a relapse:
 
⇒ YES ⇒ 11: Success (stop) [b]
 
↓
 
NO (at least one criterion not met)
 
↓
 
Patient refused all post treatment lumbar punctures
 
⇒ YES ⇒ 12: Failure (stop) [a,b]
 
↓
 
All other cases ⇒ 13. Failure
 | 
Earlier (before M18) unfavorable outcome: WBC in CSF > 50 at M6 or WBC in CSF > 20 at M12 or increasing between M6 and M12
 
⇒ YES ⇒ 9: Failure (stop)
 
↓
 
NO (no information or no earlier unfavorable assessment)
 
↓
 
Patient has clinical signs or symptoms at M18 evoking a failure
 
⇒ YES ⇒ 10: Failure (stop)
 
↓
 
NO (no clinical signs or symptoms evoking a relapse at M18)
 
↓
 
WBC in CSF ≤ 20 at M12 or in absence of LP at M12 and for both cases WBC in CSF ≤ 50 at M6 and no signs and symptoms at M18 evoking a relapse:
 
⇒ YES ⇒ 11: Success (Stop) [b]
 
↓
 
NO (at least one criterion not met)
 
↓
 
Patient refused all post treatment lumbar punctures
 
⇒ YES ⇒ 12: Failure (Stop) [a,b]
 
↓
 
All other cases ⇒ 13. Failure
 |

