| 
No lumbar puncture at M12 or no reliable count of WBC in CSF at M12 but reliable number of WBC in CSF reported later (M18 or other additional visit)
 
⇒ YES ⇒ WBC in CSF > 20 ⇒ 7: Failure (Stop)
 
⇒ YES ⇒ WBC in CSF ≤ 20 and no signs or symptoms evoking a relapse ⇒ 8: Success (Stop)
 
↓
 
NO (no later reliable count of WBC in CSF)
 
↓
 
No reliable WBC count in CSF at M12 and later and Failure at M18 for any reason
 
⇒ YES ⇒ 9: Failure at M12 (Stop)
 
↓
 
NO
 
↓
 
No reliable count of WBC in CSF at M18 and M12 but WBC counts at M6 available and no signs and symptoms evoking a failure at M12 or M18
 
⇒ YES ⇒ WBC in CSF at M6 ≤ 5 and smaller than WBC in CSF at EOH ⇒ 10: Success (stop) [b]
 
⇒ NO ⇒ WBC in CSF at M6 > 5 or larger than WBC in CSF at EOH ⇒ 11: Failure (stop)
 
↓
 
NO (no lumbar puncture at M6, M12 and M18)
 
↓
 
Patient refused all post-treatment lumbar punctures but was met at M24 or later with no signs and symptoms evoking a relapse (normal activity)
 
⇒ YES ⇒ 12: Success at M12 [b]
 
↓
 
NO (Patient not met at M24 or later)
 
↓
 
Patient refused all post treatment lumbar punctures ⇒ YES ⇒ 13: Failure (Stop) [a,b]
 | 
No lumbar puncture at M12 or no reliable count of WBC in CSF at M12 but reliable number of WBC in CSF reported later (M18 or other additional visit)
 
⇒ YES ⇒ WBC in CSF > 20 ⇒ 8: Failure (Stop)
 
⇒ YES ⇒ WBC in CSF ≤ 20 ⇒ 9: Success (Stop)
 
↓
 
NO (no later reliable count of WBC in CSF)
 
↓
 
No reliable WBC count in CSF at M12 and later and Failure at M18 for any reason
 
⇒ YES ⇒ 10: Failure at M12 (Stop)
 
↓
 
NO
 
↓
 
No reliable count of WBC in CSF at M18 and M12 but WBC counts at M6 available and no sign and symptoms evoking relapse at M12 or M18
 
YES ⇒ WBC in CSF at M6 ≤ 20 cells ⇒ 11: Success (stop) [b]
 
NO ⇒ WBC in CSF at M6 > 20 cells ⇒ 12: Failure
 
↓
 
NO (no lumbar puncture at M6, M12 and M18)
 
↓
 
Patient refused all post-treatment lumbar punctures but was met at M24 or later with no signs and symptoms evoking a relapse (normal activity)
 
⇒ YES ⇒ 13: Success at M12 [b]
 
↓
 
NO (Patient not met at M24 or later)
 
↓
 
Patient refused all post treatment lumbar punctures ⇒ YES ⇒ 14: Failure (Stop) [a,b]
 |

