
| Derivation algorithm at 6 months for stage 1 and intermediate stage | Derivation algorithm at 6 months for stage 2  |
|---|---|
|   | 
NO (no reliable count of WBC in CSF at M6, or patient did not meet at least one of the previous criteria)
↓
Patient refused all post treatment lumbar punctures
⇒ YES ⇒ 9: Failure (Stop) [a,b]
↓
Otherwise ⇒ 10: Failure
 |

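### The 12-month algorithm in SAP 10.2 has no closing Failure box, and its cohort 2 rule for a 6-month count equal to the end-of-hospitalisation count conflicts with the protocol and with SAP 10.1

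*SAP*

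**What the plan says.** **How the three algorithms end.** Both columns of SAP 10.1 (18 months) close with "All other cases ⇒ 13. Failure". In SAP 10.3 (6 months) the stage 2 column closes with "Otherwise ⇒ 10: Failure", and the cohort 2 column has an equivalent last box. In SAP 10.2 (12 months), both columns pass the label "NO (Patient not met at M24 or later" and reach one last box, which fails patients who declined every puncture after treatment. Nothing follows it.

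**Fallback when there is no usable count from 12 months on.** An 18-month failure is first carried back: "No reliable WBC count in CSF at M12 and later and Failure at M18 for any reason" gives Failure (cohort 2 box 9, stage 2 box 10). The 6-month count is used next.

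- Stage 2 boxes 11 and 12 require "WBC counts at M6 available and no sign and symptoms evoking relapse at M12 or M18", then split at 20 cells.
- Cohort 2 boxes 10 and 11 also require no signs. Box 10 is Success if "WBC in CSF at M6 ≤ 5 and smaller than WBC in CSF at EOH". Box 11 is Failure if the count is above 5 or larger than at end of hospitalisation (EOH).

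**Missing data.** SAP 7.6.1 leaves missing data for these outcomes to the algorithms themselves.

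**Protocol 2.2.2.** Late-stage success at 6 and 12 months requires absence of "signs or symptoms suggesting a relapse at the visit in question or previously". A cohort 2 patient who declines the 12-month puncture, has no signs and had 5 cells or fewer at 6 months is a probable cure; the EOH count plays no part. For cohort 2 it also says: "If no post-treatment lumbar punctures were performed, the outcome will be considered as unfavourable".

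**The concern.** If an algorithm is meant to absorb all missing data, every patient should leave it with exactly one class. After the 6-month boxes, the 12-month tree assumes that only patients with no puncture at 6, 12 and 18 months remain. That is not true of everyone who gets that far. The cohort 2 comparison with EOH is also strict on both sides, so an equal count of 5 or less fits neither box.

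The 12-month rate is a secondary objective for late-stage patients and one of two efficacy endpoints named for cohort 2. Twelve-month status also enters the repeated-measures logistic model and the trend tests in SAP 8.6.3. Safeguards are lighter here than for the primary endpoint: the pre-lock status check in SAP 6.1 refers only to the 18-month algorithm, and the double programming in SAP 12 covers only the primary endpoint. In an open-label study, a patient without a class would be settled once the data are known.

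**Working it through.** **1. Denominators.** Protocol 9.1 plans 155 late-stage patients and about 50 in cohort 2. Taking the Jeffreys interval from the quantiles of Beta(x + 0.5, n − x + 0.5), 138/155 gives 83.4% to 93.2% (width 9.8) and 146/155 gives 89.7% to 97.1% (width 7.4). Both match the protocol.

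**2. Paths that reach no box.** All patients below are alive, not lost, without rescue treatment and without trypanosomes. The counts are examples.

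| Profile | 18-month class (SAP 10.1) | Path through SAP 10.2 | 12-month class |
|---|---|---|---|
| (a) Cohort 2: EOH 2, M6 2, no count at M12 or later, no signs | Success, box 11 (no increase) | Box 9 does not fire; 2 is not smaller than 2 (box 10), and neither above 5 nor larger than 2 (box 11); boxes 12–13 need refusal of all punctures | None, or Failure if box 11 is the NO branch of box 10 |
| (b1) Cohort 2: no M12 count, M18 count 3, relapse signs | Success, box 6 | Box 7 needs more than 20; box 8 needs no signs; boxes 9–11 need no later count | None |
| (b2) Cohort 2: EOH 5, M6 1, no count at M12 or later, signs at M12 only | Success, box 11 | Box 9 does not fire; boxes 10–11 need no signs | None |
| (c) Stage 2: M6 count 50 or less, no count at M12 or later, signs at M12 only | Success, box 11 | Box 10 does not fire; boxes 11–12 need no signs; boxes 13–14 need refusal of all punctures | None if box 6 ties signs to an M12 count of 20–50; Failure if signs count on their own |

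**3. Paths that are closed.**

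- Signs at M18 with no count from M12 on: Failure at 18 months (box 10), carried back to 12 months.
- Cohort 2, equal counts above 5, no signs and no count from M12 on: Failure at box 11.
- Cohort 2 with a reliable M12 count: box 5 or 6, whatever the signs.
- Stage 2 with no M12 count but a later one: box 8 or 9, whatever the signs.

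**4. The tie (a) across the texts.**

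- Protocol 2.2.2: success, since the 6-month count is 5 or less and there are no signs.
- SAP 10.1 box 11: success, since there is no increase.
- SAP 10.2: no class or Failure.
- SAP 10.3 cohort 2 box 5: also requires a count below EOH, so the same patient is a Failure at 6 months. Protocol 2.2.2 asks only for 20 cells or fewer with no trypanosomes, rescue treatment or signs.

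**5. Size.** The documents do not give the number affected, k; k = 1 to 5 is an assumption. So are 3 other failures in cohort 2 and 9 in stage 2.

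Sign-positive patients, left out versus counted as failures:

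| | k = 1 | k = 3 | k = 5 |
|---|---|---|---|
| Cohort 2, n = 50 | 46/49 = 93.9% vs 46/50 = 92.0% (1.9) | 44/47 = 93.6% vs 44/50 = 88.0% (5.6) | 42/45 = 93.3% vs 42/50 = 84.0% (9.3) |
| Stage 2, n = 155 | 145/154 = 94.2% vs 145/155 = 93.5% (0.6) | 143/152 = 94.1% vs 143/155 = 92.3% (1.8) | 141/150 = 94.0% vs 141/155 = 91.0% (3.0) |

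One tied cohort 2 patient, with 3 other failures: as a success 47/50 = 94.0%; left out 46/49 = 93.9% (−0.1); failed 46/50 = 92.0% (−2.0).

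**The case against.** **Ties may be classified.** Cohort 2 boxes 10 and 11 are laid out as the YES and NO arms of one question, so a tie can be read as NO and hence Failure, as in 10.3. That reading is fair. It fills the gap but fails a patient whom the protocol and SAP 10.1 both call a success, so the rule needs changing either way.

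**Stage 2 may have no gap.** The last clause of box 6 can be read as failing any patient with signs. Group (c) then disappears, and no other open stage 2 path was found. This stands. The printed stage 2 numbering also goes from 6 to 8. I treat box 7 as lost in extraction, assume it classes a reliable M12 count of 20 or less as Success, and do not count it as a gap.

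**Failure is not clearly the protocol class for every sign-positive patient.** For cohort 2 without a 12-month puncture, protocol 2.2.2 uses the 18-month outcome, so signs at M12 followed by a clean M18 could be a success. The first 12-month definition in that section has no signs condition. This stands: Failure is a choice to be stated, not one that the protocol forces in all cases.

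**Stronger readings that the documents do not support.**

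- A reader might infer that patients with relapse signs generally lose their 12-month outcome. Step 3 shows that most are classified.
- A reader might infer that unclassified patients leave the denominator and push the rate up. The template in SAP 9.2.14 has a Missing row but states no percentage base, and the SAP is otherwise silent. The validation in SAP 12 would probably expose such patients. Ties left out or failed lower the rate.
- A reader might infer that the boxes for patients met at M24 turn refusers into successes. They conflict with protocol 2.2.2, but stage 2 box 13 is pre-empted by the carried-back 18-month failure. Cohort 2 box 12 is reached only if 18-month box 11 is taken as met without a 6-month count.

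**Conclusion.** SAP 10.2 is incomplete where 10.1 and 10.3 are complete, and its cohort 2 tie rule disagrees with protocol 2.2.2 and with SAP 10.1 on either reading. The two sign-positive cohort 2 groups have no stated 12-month class. The stage 2 group is conditional on box 6.

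The effect is confined to the secondary 12-month rate and the analyses that use 12-month status. One patient is worth about 0.6 points in stage 2 and about 2 points in cohort 2. For scale, the interval for 46/50 runs from 82.1% to 97.2%. The larger differences in the size table need several affected patients, for which the documents give no basis. The net direction is undetermined: leaving out sign-positive patients raises the rate relative to failing them, while leaving out or failing ties lowers it. This is an inexpensive correction to a secondary endpoint, with no bearing on the primary result.

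**What to change.** 1. In SAP 10.2 cohort 2 box 10, replace *smaller than* the EOH count with *not larger than*, in line with box 11 of 10.1.
2. Reconcile the same strict comparison in SAP 10.3 cohort 2 box 5, so that one tied 6-month count is not Failure at 6 months and Success at 12.
3. After these changes, end both columns of 10.2 with a box that classes all other cases as Failure, as in 10.1 and 10.3. Added without step 1, this box would fail the ties. State explicitly that it covers cohort 2 patients with signs and a later count of 20 or less, and those with signs at M12 only; if a clean 18-month outcome is meant to override signs at M12, say so.
4. State whether signs in stage 2 box 6 count on their own or only with an M12 count of 20–50.
5. Optionally delete cohort 2 box 12 and stage 2 box 13. This is tidying only.

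The cost is a few lines of SAP text and the matching program changes, with no new data. The 12-month rate may move slightly in either direction.

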### 10.3. Outcome at 6 months

| Derivation algorithm at 6 months for stage 1 and intermediate stage  | Derivation algorithm at 6 months for stage 2  |
|--|---|
| 
Patient is ⇒ 1: Dead (any reason of death and any time between drug intake and M6)
⇒ (definitive) Failure (stop)
 
↓
 
Alive
 
↓
 
Patient requires rescue medication for HAT at M6 or before
 
⇒ YES ⇒ 2: (definitive) Failure (stop)
 
↓
 
NO rescue medication so far
 
↓
 
Evidence of trypanosomes in any body fluid at M6 or between drug intake and M6 visit
 
⇒ YES ⇒ 3: (definitive) Failure (stop)
 
↓
 
NO observed trypanosomes so far
 
↓
 
Patient Lost to follow-up
 
⇒ YES ⇒ 4: Failure (Stop) [a,b]
 
↓
 
NO (no survival information at M6 and later)
 
↓
 
Non-hemorrhagic lumbar puncture and WBC in CSF at M6 ≤ 20 cells and smaller than that counted at EOH and no signs and symptoms evoking a relapse
 
⇒ YES ⇒ 5: Success (stop) [b]
 
↓
 
NO (at least one criterion is not met)
 
↓
 
No reliable count of WBC in CSF at M6 or WBC in CSF at M6 > 20 cells or signs and symptoms evoking a relapse
 
⇒ YES ⇒ 6: Failure
 
↓
 
Otherwise ⇒ 7: Failure
 | 
Patient is ⇒ 1: Dead (any reason of death and any time between drug intake and M6)
⇒ (definitive) Failure (stop)
 
↓
 
Alive
 
↓
 
Patient requires rescue medication for HAT at M6 or before
 
⇒ YES ⇒ 2: (definitive) Failure (stop)
 
↓
 
NO rescue medication so far
 
↓
 
Evidence of trypanosomes in any body fluid at M6 or between drug intake and M6 visit
 
⇒ YES ⇒ 3: (definitive) Failure (stop)
 
↓
 
NO observed trypanosomes so far
 
↓
 
Patient Lost to follow-up
 
⇒ YES ⇒ 4: Failure (Stop) [a,b]
 
↓
 
NO (no survival information at M6 and later)
 
↓
 
Non-hemorrhagic lumbar puncture and WBC in CSF at M6 ≤ 20 cells and no signs and symptoms evoking a relapse
 
⇒ YES ⇒ 5: Success (stop) [b]
 
↓
 
NO (no reliable count of WBC in CSF at M6 or WBC in CSF at M6 > 20 cells)
 
↓
 
Non-hemorrhagic lumbar puncture and WBC in CSF at M6 > 50 cells ⇒ YES ⇒ 6: Failure (stop)
 
↓
 
NO (no reliable count of WBC in CSF at M6 or WBC in CSF at M6 ≤ 50 cells)
 
↓
 
Non-hemorrhagic lumbar puncture and WBC in CSF at M6 > 20 but ≤ 50 cells and no further lumbar puncture or increase of WBC in CSF at M12 or failure at M12 or M18 ⇒ YES ⇒ 7: Failure (stop)
 
↓
 
NO (no reliable count of WBC in CSF at M6, or patient did not meet the previous criterion)
 
↓
 
Non-hemorrhagic lumbar puncture and WBC in CSF at M6 > 20 but ≤ 50 cells and decrease of WBC in CSF between M6 and M12 and no signs and symptoms evoking relapse at M6 and Success at M12 (if status available)
 
⇒ YES ⇒ 8: Success (stop) [b]
 
↓
 |

| Derivation algorithm at 6 months for stage 1 and intermediate stage | Derivation algorithm at 6 months for stage 2  |
|---|---|
|   | 
NO (no reliable count of WBC in CSF at M6, or patient did not meet at least one of the previous criteria)
↓
Patient refused all post treatment lumbar punctures
⇒ YES ⇒ 9: Failure (Stop) [a,b]
↓
Otherwise ⇒ 10: Failure
 |

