**Table 1 - Clinical Classification of Patients**

Visit	Ideal timing of visit after end of treatment	Favourable outcome	Uncertain outcome	Probable relapse	Proven relapse
D11	$\pm 1$ day	
 
Patient alive with no evidence of trypanosomes in any body fluid (23)
 
			
 
Evidence of trypanosomes in any body fluid
 

3 months	3 months $\pm 1$ week	
 
Patient alive with no evidence of trypanosomes in any body fluid (no lumbar puncture at 3 months unless Investigator suspects a relapse)
 
	
 
Any reason prompting the Investigator to request an additional follow-up visit
 
	
 
Neurological signs or symptoms leading to use of rescue treatment
 
	
 
Evidence of trypanosomes in any body fluid
 

6 months	6 months $\pm 2$ weeks	
 
Patient alive with no evidence of trypanosomes in any body fluid and CSF WBC <math>\leq 20/\mu\text{L}</math>
 
	
 
CSF WBC between 20 and <math>50/\mu\text{L}</math> and additional visit requested within 1-3 months
 
Any reason prompting the Investigator to request an additional follow-up visit
 
	
 
CSF WBC <math>\geq 50/\mu\text{L}</math>
 
Neurological signs or symptoms leading to use of rescue treatment
 
	
 
Evidence of trypanosomes in any body fluid
 

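### SAP 10.3 derives the month-6 outcome by rules that differ from protocol 2.2.2 and are not declared in SAP Section 11; its resampling flags also conflict with SAP 7.6.1

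*SAP*

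**What the plan says.** **Protocol 2.2.2.** An early- or intermediate-stage patient "will be considered as a success at 6 months and at 12 months if the CSF WBC is equal to or less than 20" cells/µL, with no trypanosomes, rescue treatment or suggestive symptoms. No comparison with an earlier count is made. If such a patient "does not have a lumbar puncture at 6 months, the outcome at 12 months and, if necessary, at 18 months will be used". Where nothing was sampled after dosing, this cohort's rule reads: "If no post-treatment lumbar punctures were performed, the outcome will be considered as unfavourable." For late stage, the patient "will be considered as a success at 6 months and at 12 months if the CSF WBC is equal to or below 20" cells/µL, under the same other conditions. "If the patient does not have a lumbar puncture at 6 months, the outcome of the lumbar puncture at 12 months will be used." Its late-stage counterpart for someone never sampled after dosing reads: "If the patient has no post-treatment lumbar puncture, s/he will be considered as a failure."

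**Protocol Table 1 (Section 5.4), 6 months.** A count of 20 or less is favourable. A count between 20 and 50 "and additional visit requested within 1-3 months" is an uncertain outcome.

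**SAP 10.3, stage 1 and intermediate column.** Step 5 is the only Success. It needs a non-haemorrhagic puncture, "WBC in CSF at M6 ≤ 20 cells and smaller than that counted at EOH", and no symptoms of relapse. Step 6 makes an unreliable or absent month-6 count a Failure. Step 7 makes everyone else a Failure.

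**SAP 10.3, stage 2 column.** Step 5 is Success at 20 or less. Step 8 is Success at 21-50 if the count falls by month 12 and month 12 is a Success. Step 9 fails patients who refused every post-treatment puncture. Step 10 fails the rest, which includes a missing month-6 count followed by a later puncture.

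**Flags.** In 10.3, [b] (resample in the fair-case analysis) is attached to lost to follow-up, to step 5 in both columns, and to stage 2 steps 8 and 9. SAP 7.6.1 resamples patients lost to follow-up, those who refused all post-treatment punctures, and those without a count at the visit and without proven success at another.

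**SAP Section 11** lists changes to adverse-event counting, stage wording and the yardstick only.

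**The concern.** The SAP would compute a month-6 endpoint that is not the one the protocol defines, and the report would not say so.

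Early-stage patients enter with 5 cells/µL or fewer (protocol 4.2), so their counts have little room to fall. Failing an unchanged count of 0 or 2 labels a patient with no sign of disease as a treatment failure. Failing a missing month-6 count discards the later puncture that the protocol says to use.

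The month-6 outcome feeds the month-6 success rates and their sensitivity analyses in both cohorts (SAP 8.6.2). It is also the reference visit of the mixed model (SAP 8.6.3). For stage 1 and intermediate patients, SAP 10.1 and 10.2 accept any observed count of 20 or less at months 18 and 12. Part of any rise from month 6 could therefore be a change of definition.

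The misplaced flags add a second problem: a programmer who follows them and one who follows 7.6.1 would run different fair-case analyses.

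**Working it through.** **Inputs.** Protocol 2.2.2 and Table 1; SAP 10.1, 10.2, 10.3 and 7.6.1. The rules are run side by side for a patient who is alive, not rescued, parasite-free, symptom-free and not lost to follow-up. Counts are CSF white cells/µL. The EOH count is taken to be the Day 11 puncture, the only one scheduled in hospital after treatment.

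*Stage 1 and intermediate*

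| EOH | M6 | Later puncture | Protocol 2.2.2 | SAP 10.3 |
|---|---|---|---|---|
| 3 | 2 | – | Success | Success (step 5, [b]) |
| 2 | 2 | – | Success | Failure (step 7) |
| 1 | 2 | – | Success | Failure (step 7) |
| 0 | 0 | – | Success | Failure (step 7) |
| none | 2 | – | Success | Failure (step 7) |
| 3 | none | M12 = 2 | Success | Failure (step 6) |
| 3 | none | M18 = 2 only | Success | Failure (step 6) |
| 15 | none | none | Failure | Failure (step 6) |

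No count is smaller than 0, so a patient with 0 cells at EOH can never be a month-6 Success. With 1 cell at EOH, only 0 qualifies. Neither statement needs an assumption.

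*Stage 2*

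| M6 | Later puncture | Protocol 2.2.2 | SAP 10.3 |
|---|---|---|---|
| 10 | M12 = 5 | Success | Success (step 5, [b]) |
| 30 | M12 = 10 | not a Success | Success (step 8, [b]) |
| 60 | M12 = 10 | not a Success | Failure (step 6) |
| none | M12 = 5 | Success | Failure (step 10) |
| none | none | Failure | Failure (step 9 if all refused) |

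The missing-count conflict arises only when a later puncture exists. With none, both texts give Failure.

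**Flags.** Step 5 in both columns and stage 2 step 8 all require a reliable month-6 count, yet carry [b]. The missing-count endings (stage 1/intermediate step 6, stage 2 step 10) carry none. The stage 1/intermediate column has no refused-all-punctures ending, although 7.6.1 names those patients in both the fair-case and best-case methods. Stage 2 step 9 agrees with 7.6.1.

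**Scale.** The Jeffreys interval is taken from Beta(x + 0.5, n − x + 0.5). As a check on protocol 9.1:
- 89% of 155 gives 83.4-93.2%, as stated.
- 89% of 200 gives 84.1-92.8%, as stated.
- For 50 patients the width is 15.9 points at 91% and 16.6 points at 45/50, against a stated order of 17%.

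Then:
- One patient in 50 is 100/50 = 2 points. One stage 2 patient in 155 is 100/155 = 0.65 points.
- At 95% of 50 (x = 47.5) the width is 12.5 points and the half-width 6.2. 6.2/2 = 3.1, so about three misclassified patients.
- Illustration, assuming 46/50 (92%, lower bound 82.1%) under the protocol rule: reclassifying 1, 5 or 10 patients gives 90%, 82% or 72%, with lower bounds 79.5%, 69.7% and 58.6%. How many would be reclassified is not known.

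**The case against.** **The EOH comparison has a rationale.** Every stage 1 and intermediate patient enters at 20 cells or fewer, so the threshold alone cannot show change. The SAP compares with EOH elsewhere for this cohort (10.1 steps 9 and 11; 10.2 step 10), and protocol 2.2.2 uses 5 or less at month 6 as a fallback condition. This supports some declared comparison. It does not support failing ties or a missing EOH count: 10.1 penalises only an increase, and 10.2 step 10 applies only when the month-12 and month-18 counts are both absent.

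**Step 8 looks deliberate.** The protocol's time-to-failure endpoint uses more than 50 at month 6. Protocol Table 1 calls 20-50 and falling favourable at 12 months. SAP Table 6 has a similar look-ahead for the third futility analysis, and SAP 10.1 stage 2 step 11 accepts up to 50 at month 6. A reader might infer that step 8 is an error to be reversed; these provisions do not bear that out. None of them redefines the month-6 success rate, so a reconciliation or declaration is still needed.

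**The flags are internal to the SAP.** Protocol 9.8 leaves sensitivity methods to the SAP, so the flag conflict is not a protocol change owed to Section 11. A reader might also infer that the best-case analysis cannot reach stage 1/intermediate patients who refused all punctures. That goes too far: 7.6.1 names them in its own text and can be applied without a flag. The contradiction between flags and text remains.

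**Part is already visible.** The observed-case analysis sets patients with missing month-6 data to missing, so it would show part of the effect of failing them. It does not use the later puncture, and it does not touch the EOH rule or step 8.

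**Conclusion.** The point stands for the month-6 outcome. The strict fall from EOH and the failing of missing counts are clear departures from protocol 2.2.2, and they carry most of the weight. Step 8 is a probably intended departure that is undeclared. The flags are an inconsistency between SAP 10.3 and 7.6.1.

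Three stronger readings are not supported:
- **That the trial's main result is at risk.** The primary endpoint uses SAP 10.1 and is unaffected. For early and intermediate stage, protocol 2.2.2 names months 12 and 18 as the two efficacy endpoints.
- **That the bias is known to be large.** The documents give no distribution of CSF counts and no rate of missing punctures. Only the per-patient effect is firm: 2 points in about 50 patients and 0.65 in 155. The figure of about three patients for a half-width assumes 95% success.
- **That every month-6 contrast is inflated.** In stage 1 and intermediate the two departures both lower the month-6 rate. In stage 2 the missing-count rule lowers it and step 8 raises it, so the net direction is not established.

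The correction should be made before analysis, with the weight proper to secondary analyses.

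**What to change.** In SAP 10.3:

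1. Delete the EOH comparison from stage 1/intermediate step 5. Alternatively, keep a version that fails neither ties nor a missing EOH count, and declare and justify it in Section 11.
2. With no reliable month-6 count, apply the protocol rule to the month-12 puncture itself and then, for early and intermediate stage, to the month-18 puncture. For late stage, protocol 2.2.2 names only month 12 for a missing month-6 puncture, so state whether month 18 is used if month 12 is also missing. Do not carry back the SAP 10.2 status: its step 12 (stage 1/intermediate) and step 13 (stage 2) give Success to a patient who refused every puncture but was seen well at month 24 or later. Keep patients with no post-treatment puncture as Failure.
3. Add a refused-all-punctures ending, Failure [a,b], to the stage 1/intermediate column. Use one definition of refusing all post-treatment punctures, stating whether Day 11 counts, in SAP Section 5, 7.6.1, 10.1, 10.2 and 10.3.
4. Move [b] from step 5 (both columns) and stage 2 step 8 to the endings that 7.6.1 names.
5. Reconcile stage 2 step 8 with protocol 2.2.2, or declare it and report how many patients depend on it.
6. List every retained departure from the protocol in Section 11.

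The cost is SAP text and a few lines of derivation code. Data collection and the primary analysis do not change.
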